**Study Endpoints:** The general safety endpoints are all health outcomes resulting in an emergency room visit or hospitalization in each of the following time periods immediately after vaccination (referred to as "risk periods") as follows: Days 1-60, Days 1-14, and Day 0 (for the conditions identified in secondary objective 3). These health outcomes will be grouped into pre-defined categories, using the Healthcare Cost and Utilization Project (HCUP) coding structure. HCUP is a comprehensive and well-established grouping structure that offers a pre-specified hierarchical grouping of all ICD-9 diagnosis codes into a manageable number of clinically meaningful categories.

Protocol/Amendment No.: 070-01

For the autoimmune analysis (secondary objective 2), all pre-specified new onset conditions occurring within 180 days after any dose, as identified from outpatient, emergency room visits, or hospitalizations, will be evaluated.

**Comparison Groups**: For the analysis of general safety, the recipients of GARDASILTM will serve as their own "controls" for any health outcome identified from emergency room visits and hospitalizations. For each general safety health outcome, the incidence rate of the health outcome observed during a post-vaccination self-comparison period will serve as a background rate to which the incidence rate observed in the risk periods immediately following vaccination will be compared. For the Day 1-14 and Day 0 risk period analyses, the post-vaccination self-comparison period will include a health care visit during that period to the extent possible.

For the autoimmune analysis, the comparison group will be an age-matched population of males from the health plan, not vaccinated with GARDASIL TM within the time period during which the autoimmune cases were vaccinated.

**Data Analysis:** For the general safety and autoimmune cohorts, descriptive statistics will be summarized in the study reports. When either the Regimen Initiator or Regimen Completer cohort accrues at least 22,000 males, incidence and relative risks will also be calculated. A multiplicity adjustment will be applied to take into account the large number of comparisons being made. However, all results (adjusted and unadjusted) will be included in study reports.

For the autoimmune analysis, incidence and relative risks will also be calculated. Propensity score matching is expected to be used for the background autoimmune comparison cohort.

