## General Safety Cohorts: Example of Risk Periods and Post-Vaccination Self-Comparison Periods

(Length and timing of actual periods will vary according to number of doses received and vaccination schedule of each study subject)

\*Post-vaccination self-comparison person-time will begin 91 days after each dose, thus allowing a 60-day risk window and 30-day "washout" period after each dose. In this example, the post-vaccination self-comparison time is the combined time of month 5-6 and 9-14.

ICD-9 diagnosis codes listed in any position (primary or secondary) in the database for an emergency room visit or a hospitalization occurring during the risk (or self-comparison) periods will be included in the general safety analysis, irrespective of whether it is a new diagnosis code for the patient or corresponds to a pre-existing condition or a prior episode of the health outcome. In addition, to provide interpretation context for the SRC for the primary general safety objective, the analysis will be re-run excluding chronic pre-existing conditions. The methods and decision rules for identifying and excluding chronic pre-existing conditions will be described in the study's Data Analysis Plan. The subject would still be included in analyses of all other health outcomes for which he does not have a pre-existing condition.

To facilitate the analysis and interpretation of results, all ICD-9 diagnosis codes listed for emergency room visits and hospitalizations occurring during the risk or self-comparison periods will be grouped into pre-defined health outcome categories, using the Healthcare Cost and Utilization Project (HCUP) coding structure [5]. HCUP is a comprehensive and well-established grouping structure that offers a pre-specified hierarchical grouping of all

ICD-9 diagnosis codes into a manageable number of clinically meaningful categories. The specific HCUP categories and subcategories of interest for this study will be prespecified before any analysis is performed, with concurrence from the SRC.

For events occurring on the date of vaccination (Day 0), emergency room visits and hospitalization health outcomes of interest will be limited to pre-specified, syncope, convulsive syncope; epilepsy, convulsions; head trauma; and allergic reactions. These Day 0 health outcomes of interest were pre-specified based on consideration of temporal and biological plausibility for an association with an injection or vaccination.

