For analyses associated with Day 0 (Secondary Objective 3) and Day 1-14 health outcomes (a sub-analysis for the Primary Objective and Secondary Objective 1), a selfcomparison period of 180 days in length would create an extremely uneven length of follow-up between the risk and comparison period and is expected to result in an imbalance of chance significant findings (i.e., more chance findings suggesting an increased risk following GARDASILTM) [6]. Therefore, an attempt will be made to balance the length of the risk periods in the analysis in the Day 0 and Day 1-14 analyses. The opportunity to have had a healthcare visit during the post-vaccination selfcomparison period will be taken into consideration. For example, a day on which a doctor visit occurred during the self-comparison period will be used for outcome assessment for Day 0 analyses. Similarly, for the Day 1-14 analyses, the self-comparison period will be 14 days following the date associated with a physician visit if such visit occurred in the relevant time period. This approach will be further detailed in the study's Data Analysis Plan and may include use of simulations or developing similar length comparison periods. The methods will be finalized prior to undertaking any statistical analysis of the data.

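### The Day 0 and Day 1-14 comparators are anchored on a doctor visit that need not resemble a vaccination visit, so the relative risk may be biased toward or below 1, most of all on Day 0.

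*Protocol*

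**What the plan says.** Section 3.7.1 explains that a 180-day reference would be far longer than the Day 0 and Day 1-14 risk periods and would tilt chance findings toward apparent harm. It therefore balances the lengths. It adds that the chance of having had a healthcare visit "will be taken into consideration". The Day 0 rule follows, introduced as an example: "a day on which a doctor visit occurred during the self-comparison period will be used for outcome assessment for Day 0 analyses". For Days 1-14, "the self-comparison period will be 14 days following the date associated with a physician visit if such visit occurred in the relevant time period". The Synopsis puts it more loosely: "the post-vaccination self-comparison period will include a health care visit during that period to the extent possible".

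The details are left open: "This approach will be further detailed in the study's Data Analysis Plan and may include use of simulations or developing similar length comparison periods". Methods are to be settled before any analysis.

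Section 3.6.1 restricts Day 0 to acute events: "emergency room visits and hospitalization health outcomes of interest will be limited to pre-specified, syncope, convulsive syncope; epilepsy, convulsions; head trauma; and allergic reactions". It says of this list: "These Day 0 health outcomes of interest were pre-specified based on consideration of temporal and biological plausibility". The same section counts diagnosis codes in any position, whether new or pre-existing. Section 3.5 says vaccine is given in routine care. Section 4.1.2 defines the relative risk as incidence in the risk period over incidence in the self-comparison period.

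Nowhere does the protocol limit the anchor by reason for visit, or say whether an emergency encounter may serve as one.

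**The concern.** The anchor is meant to give the comparator the same opportunity for care as a vaccination day. A visit of unspecified type equalises the fact of a visit but not its reason. A vaccination visit is usually planned. A visit in the self-comparison time may have been made because something was wrong, and on such days emergency and hospital diagnoses are more frequent.

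For Day 0 the difficulty is sharper. A subject who faints or has a seizure may see a doctor that same day. The visit makes the day eligible as comparator, and the event is counted on it, so the outcome helps choose its own reference day.

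For Days 1-14 the window starts after the visit, so an event on the visit day need not count. What remains is carry-over of the same episode, or repeat coding of a known condition, which is a weaker route.

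An inflated denominator lowers the relative risk. In a safety study that direction can hide harm, here in outcomes chosen because a link with injection is plausible.

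**Working it through.** No figure in the protocol depends on the visit anchor, so there is nothing to reproduce. The check is of direction, and of how strong the assumptions must be.

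**Model.** Let s be the share of comparator anchor visits prompted by illness or injury, v the same share among vaccination visits, and k the outcome rate at an illness visit relative to a well visit. None of the three is in the documents; all are assumptions. Then

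observed RR = true RR × (1 − v + v·k) / (1 − s + s·k).

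The ratio is below 1 whenever s > v and k > 1, and equals 1 when s = v.

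**Illustration.** With s = 0.50, v = 0, k = 3 the denominator is 0.50 + 1.50 = 2, so a true RR of 2 shows as 2/2 = 1.0 and a true RR of 1 shows as 0.50.

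**Range for a true RR of 2, v = 0**

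| s | k = 2 | k = 3 | k = 5 |
|---|---|---|---|
| 0.25 | 1.60 | 1.33 | 1.00 |
| 0.50 | 1.33 | 1.00 | 0.67 |
| 0.75 | 1.14 | 0.80 | 0.50 |

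The k at which the observed RR falls to 1 is 1 + (true RR − 1)/s. For s = 0.25, 0.50 and 0.75 this is 5.0, 3.0 and 2.3 for a true RR of 2, and 9.0, 5.0 and 3.7 for a true RR of 3.

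**If some vaccination visits are also illness visits** (true RR 2, s = 0.50, k = 3):

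- v = 0.1: 2 × 1.2/2 = 1.2
- v = 0.2: 2 × 1.4/2 = 1.4
- v = 0.5: 2 × 2/2 = 2.0, no bias

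**How few events matter on Day 0.** Take the most frequent background in Table 4-2, 1 per 2,000 in two months, and 132,000 comparator windows of 60 days with one anchor day each (assumed for a Day 0 outcome). The windows hold 132,000/2,000 = 66 events, and the anchor days 66/60 = 1.1 by chance. If 1.1 of the other 64.9 events (1.7%) brought their own day in as anchor, the reference count would double and the RR would halve, provided vaccination days carry no such events.

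**Equal-length windows.** Null tail rates of the mid-P test (two-sided 0.05, 132,000 windows, backgrounds from Table 4-2):

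| Background | Risk : comparator days | Upper tail | Lower tail |
|---|---|---|---|
| 1/12,000 | 14 : 14 | 1.3% | 1.3% |
| 1/12,000 | 14 : 180 | 2.3% | 1.0% |
| 1/20,000 | 14 : 14 | 0.5% | 0.5% |
| 1/20,000 | 14 : 180 | 2.1% | 0.0% |

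The long reference gives the one-sided excess of chance findings that Section 3.7.1 describes.

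**The case against.** The strongest reply is that the protocol does not fix the rule. The Day 0 wording is an example, it does not say that every visit qualifies, and the detail goes to a Data Analysis Plan that is not shown and may restrict visit type. That stands against any statement that the reference rate is inflated. It does not dispose of the point, because the only criterion the protocol gives is that a visit took place, and a plan written to it literally would carry the bias.

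Second, the bias needs comparator visits to be illness-driven more often than vaccination visits, and no visit mix is given. This also stands: the inequality is plausible but undocumented.

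Third, Day 0 is a secondary objective and Days 1-14 a sub-analysis, and Section 3.3 lets the Safety Review Committee weigh timing and plausibility and request record review. That limits the consequence. However, a relative risk pulled to 1 is less likely to prompt such a review.

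Two stronger readings are tempting and unsupported. A reader might infer that even a very large vaccination-day risk would look strongly protective, by supposing that 0.1% of anchor visits bring an outcome event. That adds 132 events, twice the 66 that the assumed background allows in all the windows. A reader might also infer that the exact method makes equal-length windows unnecessary. The tail rates show that the imbalance is real. A longer reference would add power, but that is a trade-off and not an error in the plan.

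**Conclusion.** The point holds as a conditional bias. Section 3.7.1 anchors both short-window comparators on a doctor visit without requiring that it match a vaccination visit in type. If comparator visits are illness-prompted more often, the Day 0 relative risk, and to a lesser degree the Day 1-14 one, may be biased toward or below 1. Under moderate assumptions the bias is enough to bring a true relative risk of 2 down to 1.0 or lower. With equal visit mixes it is nil. The actual size cannot be derived from the documents. It is worth correcting because the remedy is cheap and the error would run toward missing harm.

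**What to change.** In Section 3.7.1, define the anchor for both analyses as a preventive-care, other-immunisation or otherwise scheduled visit in the self-comparison time, chosen by visit type alone and without regard to whether the outcome occurred that day.

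- Do not use emergency or illness visits as anchors.
- Still count any outcome emergency visit or hospitalization that falls on an eligible anchor day or in its window. Discarding days because they carry the outcome code or an emergency claim would remove genuine reference events and bias the relative risk upward.
- Where a subject has no eligible visit, use a randomly chosen day or 14-day window in the self-comparison time, and report how many subjects this affects, since those days do not match the opportunity for care.
- Report the any-visit anchor as a sensitivity analysis.
- Keep the equal-length windows.

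The cost is a sentence or two in the protocol and a visit-type code list in the Data Analysis Plan, using claims already in the database. The small downside is fewer visit-anchored days.

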#### 3.7.2 Autoimmune Comparison Populations

To provide context for interpreting data on autoimmune cases identified in the risk periods, the rates of the pre-specified, new-onset autoimmune conditions will be estimated in a general cohort of age-matched males not vaccinated with GARDASILTM (background rates). Propensity score matching is expected to be used for the comparison cohort analysis.

Background rates in the general population: Background rates of the autoimmune conditions will be estimated within an age-matched population of males, from the health plan, not vaccinated with GARDASILTM within the time period during which the autoimmune cases from the vaccinated cohort were vaccinated. A sample of potential cases from the background population will be selected for case review to further refine the true incidence of each autoimmune condition in the background population. These potential background cases will be selected using similar methods as used for the autoimmune cohort (described in Section 3.6.2).

#### 3.8 REPORTING OF SERIOUS ADVERSE EXPERIENCES

No reporting of individual cases to regulatory agencies is planned as part of this retrospective observational database study. This is consistent with the Council for International Organization of Medical Sciences (CIOMS V), which states that for epidemiological studies, individual case reporting is generally not appropriate unless there is specific attribution of an individual case (i.e., within the medical record). The study results will be included in a report at the end of study. Interim reports may be provided on an annual basis to the regulatory agencies until completion of the study. Aggregate reports may be provided to regulatory agencies in the Periodic Safety Update Reports (PSUR) as soon as available.

However, since the study specifies procedures for the case review of medical records for specific health outcomes of interest, there are certain circumstances in which serious adverse experiences (SAEs), if identified, will be reported. Specifically, for cases whose medical records are reviewed, if there is written notation in the medical record indicating that a health care provider attributed a serious adverse experience to any Merck product, then would complete a serious adverse experience (SAE) report form (Attachment) and submit it within 24 hours to the Merck SPONSOR Contact by Fax or e-mail. (Note: the SAE form will not include identifying information such as names or phone numbers.) Merck Sponsor Contact will submit the SAE form to Merck Global Safety within 2 business days of receipt for reporting to worldwide regulatory agencies as appropriate.

For reference, an SAE is any adverse experience occurring at any dose that:

- †Results in death; or
- †Is life threatening (places the subject, in the view of the investigator, at immediate risk of death from the experience as it occurred; or
- †Results in a persistent or significant disability/incapacity (substantial disruption of one's ability to conduct normal life functions); or
- †Results in or prolongs an existing inpatient hospitalization (hospitalization is defined as an inpatient admission, regardless of length of stay, even if the hospitalization is a precautionary measure for continued observation) (Note: Hospitalization [including hospitalization for an elective procedure] for a preexisting condition which has not worsened does not constitute a serious adverse experience.); or
- †Is a congenital anomaly/birth defect (in offspring of subject taking the product regardless of time to diagnosis); or
- Is a cancer: or
- Is an overdose (whether accidental or intentional).

ALSO: Other important medical events that may not result in death, not be life threatening, or not require hospitalization may be considered a serious adverse experience when, based upon appropriate medical judgment, the event may jeopardize the subject and may require medical or surgical intervention to prevent one of the outcomes listed

previously (designated above by a †). Examples of such medical events include allergic bronchospasm requiring intensive treatment in an emergency room or at home and blood dyscrasias or convulsions that do not result in inpatient hospitalization.

#### 3.9 STUDY START AND END DATES

The official study start date will be the date of IRB approval at PPD targeted to be no later than 2 months after the FDA has reviewed and approved the final protocol. The study end date will be when either the targeted sample size of 135,000 Regimen Initiators or 44,000 Regimen Completers in the general safety cohort is achieved. If this sample size is not achieved within 6 years of the official study start date, the study will be ended, with the end date being the sixth anniversary of the study start date.

#### 3.10 REPORT TIMELINES AND CONTENTS

#### 3.10.1 Annual Interim Reports

A series of annual interim reports will be developed. The annual interim reports will include information generated from the study for the time period starting at the date of FDA approval for use of GARDASILTM in males (October 2009) and ending at a prespecified cut-off date. For each annual interim report, the cut-off date will be the most recent one-year anniversary of the official study start date. Each annual interim report will be submitted within six months after the most recent annual cut-off date.

Each annual interim report will include:

- the number of males accrued in the general safety and autoimmune cohorts;
- a description of the demographic, health care use and general characteristics of vaccinees, put into perspective with the general male population of the same age at PPD by age categories;
- the numbers of events for each general safety health outcome observed within the risk windows with any available follow-up time prior to the cut-off date;
- the number of electronically identified potential new-onset autoimmune cases;
   and
- the number of new-onset autoimmune cases that were confirmed by the CRC prior to the cut-off date.

When 22,000 males in the general safety cohort of Regimen Initiators (i.e., at least one dose of GARDASILTM) are accrued at least 3 months in advance of any interim annual report cut-off date, the annual interim reports will also include:

- incidence and 95% confidence intervals for general safety events (emergency room visits or hospitalizations) in the risk and self-comparison periods; and
- relative risks and 95% confidence intervals for general safety events occurring in the risk periods relative to the self-comparison periods.

The 3-month lag time is required to allow sufficient analysis time. The accrual point of 22,000 males with at least one dose was selected to provide a preliminary assessment of general safety in a manner somewhat similar to the GARDASILTM safety study for females. For females, an interim report was written after accrual and follow-up time was available for 22,000 females with 3 doses per protocol. The male population of 22,000 Regimen Initiators (rather than Regimen Completers with complete follow-up time) was selected to allow preliminary results to be presented sooner.

When 22,000 males in the Regimen Completers cohort are accrued at least 3 months in advance of any interim annual report cut-off date, preliminary results, including incidence and relative risks for this cohort will also be provided in the annual interim report, using an approach analogous to the Regimen Initiator approach described above. Once provided in an interim annual report, updated preliminary results on the Regimen Initiators and/or Regimen Completers will be provided in subsequent annual interim reports until the final report.

## 3.10.2 Final Report

A final report will be written and will include incidence and relative risk estimates for the final number of participants in the general safety and autoimmune cohorts as of the study end date. To allow for complete follow-up for general safety, database settling, and analysis time, the final report will be submitted within 24 months of the study end date, which will occur upon attainment of the target sample size or at study year 6, whichever occurs first. It is possible that a supplemental report may be needed after the final report to achieve full follow-up for deaths and/or the autoimmune population. The final report will replace the last interim report if the cut-off time for the final report is estimated to be less than 12 months apart from the cut-off time for the last interim report.

Protocol/Amendment No.: 070-01

#### 4. DATA ANALYSIS

The methods for data analysis will be detailed in the study's Data Analysis Plan. The Data Analysis Plan will describe statistical methods, data management and programming procedures and quality assurance/quality control procedures. The Data Analysis Plan will be finalized prior to undertaking any data analyses. An overview of the data analysis approach is presented in this section.

#### 4.1 DATA ANALYSIS FOR GENERAL SAFETY COHORTS

#### 4.1.1 Incidence

The incidence of all health outcomes that result in a hospitalization or emergency room visit during the risk and self-comparison periods will be described. Incidence will be calculated separately for health outcomes associated with hospitalizations and emergency room visits, as well as for hospitalizations and emergency room visits combined. For the analysis using combined hospitalizations and emergency room visits, if an emergency room visit results in a hospitalization for the same health care event, the event will be counted once to avoid duplication.

For each subject, the incidence of a health outcome in a given risk or self-comparison period will be defined as the first occurrence in the database of a code of the health outcome HCUP category, if any, during this study period. For each health outcome category, the incidence in both the risk and the post-vaccination self-comparison periods will be calculated as the number of first occurrences of the health outcome divided by the total person-time accrued from the study subjects under observation. For each event, accrued person-time for an individual will be calculated as the total number of days from the beginning of the risk or self-comparison period and ending at the earliest of: the end of the period, receipt of a subsequent dose of GARDASILTM, termination of membership in the health plan, occurrence of the health outcome of interest, death, or, for interim annual reports only, attainment of the pre-specified cut-off date for the report. A subject can have partially-missing risk or self-comparison periods and still be part of the analysis.

For analyses in which subjects may have more than one dose, each subject can contribute only once for each specific health outcome throughout the combined risk periods (i.e., maximum of one occurrence of each health outcome taken into account for each study subject). The denominator will be the combined at risk person-time accrued throughout the number of risk periods (or corresponding self-comparison periods) available for a given individual (censored upon occurrence of the outcome), which will depend on the number of doses received.

